#### 11.1.5.3 Paternal Exposure

Male subjects should refrain from fathering a child or donating sperm during the study and for 3 months following the last dose. Pregnancy of the patient's partners is not considered to be an adverse event. However, the outcome of all pregnancies (spontaneous miscarriage, elective termination, ectopic pregnancy, normal birth or congenital abnormality) should if possible be followed up and documented. The outcome of any conception occurring from the date of the first dose until 3 months *after the last dose* should be followed up and documented.

#### 11.1.6 Unexpected Adverse Event

For this study, an AE is considered unexpected when it varies in nature, intensity or frequency from information provided in the current IB, prescribing information or when it is not included in the informed consent document as a potential risk. Unexpected also refers to AEs that are mentioned in the IB as occurring with a class of drugs or are anticipated from the

Version Date: 15MAY2019 Confidential Page 50 of 60

pharmacological properties of the drug, but are not specifically mentioned as occurring with the particular drug under investigation.

#### 11.1.7 Relatedness

AEs will be categorized according to the likelihood that they are related to the study drug(s). Specifically, they will be categorized using the following terms:

Unrelated	Adverse Event is not related to the study drug(s)
Unlikely	Adverse Event is doubtfully related to the study drug(s)
Possible	Adverse Event may be related to the study drug(s)
Probable	Adverse Event is likely related to the study drug(s)
Definite	Adverse Event is clearly related to the study drug(s)

#### 11.2 Reporting

#### 11.2.1 Adverse Events

- AEs will be recorded from time of signed informed consent until 30 days after discontinuation of study drug(s) or until a new anti-cancer treatment starts, whichever occurs first.
- AEs will be recorded regardless of whether or not they are considered related to the study drug(s).
- All AEs will be recorded in the subject's medical record and on the appropriate study specific eCRF form within the EDC system.
- AEs considered related to study drug(s) will be followed until resolution to Grade ≤ 1 or baseline, deemed clinically insignificant, and/or until a new anti-cancer treatment starts, whichever occurs first.
- Transient asymptomatic laboratory abnormalities that do not require treatment will not be collected as adverse events.

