# 2.2.2 Secondary Endpoints

- Adverse events are defined by the NCI Common Terminology Criteria for Adverse Events (NCI CTCAE) v4
- Progression-free survival is defined as the time from Day 1 of treatment until the criteria for disease progression is met as defined by RECIST 1.1 or death as a result of any cause.
- Overall survival is defined as the time from Day 1 of treatment until death as a result of any cause

Version Date: 15MAY2019 Confidential Page 24 of 60

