# 7. STUDY CALENDAR & EVALUATIONS

Study Evaluation Cycle = 28 days	Screening	Treatment	Tumor	Safety Follow Up Visit 	Survival Follow Up 
	-28 days	Cycle 1 + Day 1 ± 2 days	Assessments  ± 7 days	30 Days Post Treatment (±7 days)	Every 3 Months (±7 days)
REQUIRED ASSESSMENTS					
Informed Consent	X				
Medical History 	X				
Physical Exam	X	X		X	
Vital signs and ECOG Performance Status 	X	X		X	
Documentation of DDR alteration in CLIA lab assay 	X				
ECG 	$X^4$				
AEs & Concomitant Medications	X	X		X	
LABORATORY ASSESSMENTS					
Complete Blood Cell Count with diff (CBC) 	X	X		X	
Comprehensive Metabolic Profile (CMP) 	X	X		X	
PT/INR and aPTT 	X				
Pregnancy test (serum or urine) (WOCBP) 	X	$X^7$			
Urinalysis	X				
DISEASE ASSESSMENT					
CT of chest 	X		$X^8$		
CT or MRI of abdomen and pelvis 	X		$X^8$		
Bone Scan 	X		X8		
TREATMENT EXPOSURE					
Olaparib		X			
CORRELATIVE SAMPLES					
Archival Tumor Tissue 	X				
Collection of tumor tissue obtained as standard of care 				$X^{10}$	
Blood Samples for correlative research 		$X^{11}$		$X^{11}$	
BANKING SAMPLES					
Whole Blood 		$X^{12}$		$X^{12}$	
FOLLOW-UP					
Survival Status, Subsequent Therapy					X

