# **Key to Footnotes**

- 1: Medical History should include the following information: (1) Diagnosis and staging to include Tumor Node Metastasis (TNM) staging (2) smoking history, (3) trial awareness question (4) prior cancer treatment history and (5) genetic sequencing information.
- 2: Vital signs to include blood pressure, weight, and height (screening only) and ECOG performance status.
- 3: The laboratory report indicating the presence of a DDR alteration (see eligibility) from a CLIA laboratory is required for registration.
- 4: ECG is required within 7 days prior to starting study treatment.
- 5: If screening (baseline) CBC and CMP were performed within 7 days of Day 1 of treatment, these do not need to be repeated. CMP to include sodium, potassium, chloride, creatinine, blood urea nitrogen; liver function tests (LFTs) to include AST, ALT, total bilirubin, alkaline phosphatase
- 6: Subjects taking warfarin may participate in this study; however, it is recommended that prothrombin time (INR and APTT) be monitored carefully at least once per week for the first month, then monthly if the INR is stable.
- 7: For women of childbearing potential (WOCBP): urine or serum βhCG will be checked at screening and prior to study drug on Cycle 1 Day 1 (only if clinically appropriate). If a urine test is done and it is positive or cannot be confirmed as negative, a serum pregnancy test will be required.
- 8: Tumor imaging to continue near the end of every 2nd cycle (~every 8 weeks) for the first 12 months following Cycle 1 Day 1. After 12 months, tumor assessments will be performed near the end of every 3rd cycle (~every 12 weeks). Imaging selected for each subject should remain the same throughout the study. Bone scan will be obtained at screening if there is any clinical or laboratory suspicion of metastatic bone involvement. If bone scan is positive at baseline for metastases, it will be included with tumor response assessments as noted above.

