# 11.1 Definitions

#### 11.1.1 Adverse Event (AE)

An AE is any untoward medical occurrence whether or not considered related to the study drug that appears to change in intensity during the course of the study. The following are examples of AEs:

- Unintended or unfavorable sign or symptom
- A disease temporally associated with participation in the protocol
- An intercurrent illness or injury that impairs the well-being of the subject

Abnormal laboratory values or diagnostic test results constitute AEs only if they induce clinical signs or symptoms or require treatment or further diagnostic tests

Hospitalization for elective surgery or routine clinical procedures that are not the result of an AE (e.g., surgical insertion of central line) should not be recorded as an AE.

Disease progression should not be recorded as an AE, unless it is attributable to the study regimen by the site investigator.

Version Date: 15MAY2019 Confidential Page 48 of 60

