# 12.2.2 Definition of Secondary Endpoints

- Safety of olaparib, defined as rates of Grade 1-5 toxicity according to CTCAE v4.03.
- PFS, which is defined as the time from initiation of treatment to death or progression, depending on which occurs first (as defined by RECIST 1.1).
- Overall survival (OS), which is defined as the time from initiation of treatment to death.

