# 12.4.2 Analysis Plans for Secondary Objectives

Any subject who receives at least one dose of treatment on this protocol is evaluable for toxicity, progression free survival and overall survival. Toxicity rates will be summarized using frequency tables. Progression free survival and overall survival curves will be based on the Kaplan-Meier method.

Version Date: 15MAY2019 Confidential Page 53 of 60

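### The toxicity endpoint covers all CTCAE grades, but the adverse-event rules leave out some gradable laboratory values and no analysis of the scheduled blood tests is planned

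*Combined protocol and SAP*

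**What the plan says.** Section 12.2.2 defines the endpoint: "Safety of olaparib, defined as rates of Grade 1-5 toxicity according to CTCAE v4.03". Section 2.2.2 puts the same endpoint in terms of adverse events: "Adverse events are defined by the NCI Common Terminology Criteria for Adverse Events (NCI CTCAE) v4". Section 12.4.2 takes all treated subjects as the analysis set, and its whole safety analysis is one sentence: "Toxicity rates will be summarized using frequency tables". It names no data source and plans no laboratory table.

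Two rules decide whether a laboratory finding enters the adverse-event record. Section 11.1.1: "Abnormal laboratory values or diagnostic test results constitute AEs only if they induce clinical signs or symptoms or require treatment or further diagnostic tests". Section 11.2.1: "Transient asymptomatic laboratory abnormalities that do not require treatment will not be collected as adverse events".

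The values themselves are scheduled. The Section 7 calendar has a blood count with differential and a metabolic profile at screening, on Day 1 of the treatment cycles and at the 30-day safety visit. The footnote on the profile reads "CMP to include sodium, potassium, chloride, creatinine, blood urea nitrogen", followed by liver tests. Section 14.2 says that clinical data will generally be captured in the EDC, but commits to only a selection of standard-of-care data.

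**The concern.** Section 6 grades blood counts by value alone: in Table 2 a hemoglobin below 8 g/dl is Grade 3 with no symptom condition. A result can therefore carry a CTCAE grade and still not qualify as an adverse event under Section 11. An endpoint that promises all grades would then be reported from a record from which some graded findings have been removed.

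This matters because laboratory toxicity is a large part of what is expected. Section 1.5.4 lists anemia as very common, and neutropenia, thrombocytopenia, leukopenia and creatinine increase as common. Subjects may enter with a creatinine clearance only just above 30 mL/min, so the renal profile will be of interest to readers.

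**Working it through.** **Step 1. The rules side by side.** "Section 6" below is shorthand for its introduction and Section 6.2.2.

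| Laboratory finding | Section 11.1.1 | Section 11.2.1 |
|---|---|---|
| Symptomatic, or needing treatment | adverse event | collected |
| Transient, asymptomatic, untreated, leads only to further tests | adverse event | not collected |
| Persistent, asymptomatic, needs nothing | not an adverse event | not excluded |
| Transient, asymptomatic, needs nothing | not an adverse event | not collected |
| Brief asymptomatic Grade 3-4 count, managed only by interruption | interruption not listed as a reason to record | interruption not listed as a reason to record |

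The two rules disagree in the second and third rows and both remove the fourth. In the last row, Section 6 points the other way. Its introduction includes events that lead to interruption among the adverse events to be evaluated, and Section 6.2.2 calls neutropenia and leukopenia adverse events where it directs interruption.

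**Step 2. What Section 6 keeps in.** Table 2 calls for supportive care and a search for the cause once hemoglobin is below 10 g/dl. Table 3 names the same in its Grade 1-2 row for neutrophils, leukocytes and platelets. Section 6.3.3 asks for a retest if clearance falls below the entry threshold. Findings handled this way meet Section 11.1.1. What remains exposed is mainly Grade 1 hemoglobin (Table 2 has no row at or above 10 g/dl), Grade 1 counts on which the site takes no action, and low-grade creatinine rises.

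**Step 3. Illustration from the plan's own tables.** Section 1.5.4 gives separate adverse-reaction and laboratory tables for the olaparib arm of a randomised ovarian cancer trial. Expected subjects = n × rate, with n = 27 planned and up to 30 (Section 12.3), assuming the rates carry over.

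- Hemoglobin, any grade, as adverse reaction: 27 × 0.44 = 11.9; 30 × 0.44 = 13.2.
- Hemoglobin, any grade, by laboratory value: 27 × 0.83 = 22.4; 30 × 0.83 = 24.9.
- Gap: 83 − 44 = 39 points, or 39/83 = 47% of the laboratory cases if every adverse reaction is also a laboratory case.
- Hemoglobin, Grade 3-4: 17% by laboratory value, 20% as adverse reaction; 17 − 20 = −3 points, so no shortfall.
- Neutrophils, platelets and creatinine, any grade, by laboratory value: 51%, 42% and 44%, that is 13.8, 11.3 and 11.9 of 27. None appears in the adverse-reaction table, whose cut-off is 20%, so each was presumably below 20% (27 × 0.20 = 5.4).
- Grade 3-4 by laboratory value: neutrophils 7%, platelets 2%, creatinine 0%; at most 27 × 0.07 = 1.9 subjects each.

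The fraction q of findings that would meet the exclusion is unknown. For creatinine the reported rate would be 44% × (1 − q): 44%, 33%, 22%, 11% and 0% for q = 0, 0.25, 0.5, 0.75 and 1.

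**Step 4. What does not move.** The design in Section 12.3 reproduces: with n = 27 and success at 6 or more responses, the exact test gives alpha 0.0471 at a 10% response rate and power 0.809 at 28% (stated: 0.0471 and 81%). It does not use toxicity data. The stopping limits in Section 12.5 also reproduce: the exact 95% lower bounds are 18.7% for 5/10 and 15.4% for 7/20 (cut-off 15%), and 2.5% for 2/10 and 1.2% for 2/20 (cut-off 1%). They count treatment-related serious events and the named events of special interest, which asymptomatic untreated laboratory values should rarely be.

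**The case against.** The strongest reply is that little of importance is lost. Section 11.2.1 excludes only findings that are at once transient, asymptomatic and untreated, and Section 11.1.1 keeps those needing treatment or further tests. A reader might infer that all asymptomatic laboratory abnormalities are dropped; the text does not say that, and Section 6 brings many cytopenias back in.

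A reader might also infer that Grade 3-4 counts will be lost, since a pause in dosing is not treatment. That goes too far. Section 6 treats such events as adverse events, recovery to Grade 1 can be shown only by repeat counts (arguably further tests), and Section 6.4 records every interruption and its reason in the eCRF. What stands is an ambiguity, because neither Section 11 rule mentions interruption and sites could read it differently.

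The documents do not say that adverse-event forms are the only source for the tables. Sections 12.2.2 and 12.4.2 speak of toxicity and name none, so understatement is a conditional conclusion. If the endpoint means adverse events, as Section 2.2.2 has it, then adverse-event rates answer it; but the promise of all CTCAE grades then needs qualifying.

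The 39-point gap is not an estimate of the loss here. That trial's collection rules are not described, the direction reverses at Grade 3-4, and 69% of its placebo arm also had a hemoglobin decrease. Nor is any formal comparison with those tables planned; the safety objective is descriptive. These limits stand, and they reduce the point to the completeness of a secondary endpoint.

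**Conclusion.** The mismatch between an all-grade endpoint and a restricted record is real. If the toxicity tables come from adverse-event records, any-grade hematologic and creatinine rates will tend to be too low. The direction follows from the rules; the size does not, because neither q nor the reference trial's rules are given. The reference figures show only that the two sources can differ widely at any grade and agree closely at Grade 3-4 for hemoglobin. The conclusion rests on reading Sections 2.2.2 and 12.4.2 together as pointing to adverse-event records, and on reading the calendar's treatment column as Day 1 of every cycle. The primary endpoint, sample size and alpha are untouched, and the stopping rules essentially so. The point is worth correcting because it is cheap and affects how a stated secondary endpoint will be read.

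**What to change.** In Section 12.4.2, state the source of the toxicity tables and add that hematologic and chemistry toxicity will also be graded by CTCAE v4.03 directly from the scheduled blood counts and metabolic profiles. Tabulate worst post-baseline grade and shift from baseline for all treated subjects, beside the adverse-event table. The shift table is needed because entry is allowed at a hemoglobin of 9 g/dL, which Table 2 already places in Grade 2.

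Confirm that the cycle-by-cycle values are entered in the EDC, since Section 14.2 does not guarantee it.

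Reconcile the introduction to Section 6 with Sections 11.1.1 and 11.2.1, so that it is clear whether a laboratory finding that leads only to further tests, or only to a dose interruption, is recorded as an adverse event. No dosing or management rule needs to change for this.

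The cost is one extra table, EDC entry of laboratory values if not already planned, and laboratory toxicity rates that will look higher than an adverse-event table alone.

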#### 11.2.2 Serious Adverse Events (SAEs)

# 11.2.2.1 Site Requirements for Reporting SAEs to HCRN

- SAEs will be reported from time of signed informed consent until 30 days after discontinuation of study drug(s).
- SAEs will be reported on the SAE Submission Form within 1 business day of discovery of the event.
- SAEs include events related and unrelated to the study drug(s).
- All SAEs will be recorded in the subject's medical record and on the appropriate study specific eCRF form within the EDC system.
- All SAEs regardless of relation to study drug will be followed until resolution to ≤ Grade 1 or baseline and/or deemed clinically insignificant and/or until a new anti-cancer treatment starts, whichever occurs first.

Version Date: 15MAY2019 Confidential Page 51 of 60

The site will submit the completed SAE Submission Form to HCRN within 1 business day of discovery of the event. The form may be submitted to HCRN electronically to [contact]. The site investigator is responsible for informing the IRB and/or other local regulatory bodies as per local requirements.

The original copy of the SAE Submission Form and the email correspondence must be kept within the study file at the study site.

Once the SAE has resolved (see resolution guidelines listed in 11.2.2.1), sites must submit a follow-up SAE Submission Form within a reasonable timeframe to HCRN electronically to [contact].

#### 11.2.2.2 HCRN Requirements for Reporting Events to AstraZeneca

HCRN will report all SAEs, AESIs, and other reportable events to AstraZeneca within 1 business day of knowledge of the event. Follow-up information will be provided to AstraZeneca as reasonably requested.

Serious adverse events that do not require expedited reporting to the FDA still need to be reported to AstraZeneca, preferably using the MedDRA coding language for serious adverse events. This information should be reported on a monthly basis and under no circumstance less frequently than quarterly.

Send SAE report and accompanying cover page by way of email to AstraZeneca's designated mailbox: [contact].

#### 11.2.2.3 Sponsor-Investigator Responsibilities

HCRN will send a SAE summary to the sponsor-investigator **within 1 business day** of receipt of SAE Submission Form from a site. The sponsor-investigator will promptly review the SAE summary and assess for expectedness and relatedness.

## 11.2.2.4 HCRN Responsibilities to FDA

This protocol was deemed exempt by the FDA 10/27/17. For protocols exempt from the requirements of an IND, the above stated requirements are not applicable. HCRN will continue to facilitate compliance of applicable requirements for the sponsor-investigator in relation to this study. This includes but is not limited to 21 CFR 50.20 informed consent, 21 CFR Part 56 IRB, and pertinent sections of the Public Health Service Act and FDAAA.

#### 11.2.2.5 IND Safety Reports Unrelated to this Trial

AstraZeneca will provide to HCRN IND safety reports from external studies that involve the study drug(s) per their guidelines. HCRN will forward safety reports to the sponsor-investigator who will review these reports and determine if revisions are needed to the protocol or consent. HCRN will forward these reports to participating sites **within 1 business day** of receiving the sponsor-investigator's review. Based on the sponsor-investigator's review, applicable changes will be made to the protocol and informed consent document (if required). All IND safety reports will also be made available to sites via the EDC system.

Version Date: 15MAY2019 Confidential Page 52 of 60

Upon receipt from HCRN, site investigators (or designees) are responsible for submitting these safety reports to their respective IRBs, as per their IRB policies.

#### 12 STATISTICAL METHODS

# 12.1 Study Design

This is a single arm open label multi-institutional phase II trial of olaparib monotherapy in subjects with metastatic urothelial cancer harboring somatic DDR alterations. The primary objective of the study is to estimate the objective response rate (per RECIST 1.1 or MD Anderson criteria for bone-only metastases) to treatment with olaparib.

# 12.2 Endpoints

# 12.2.1 Definition of Primary Endpoint

The primary endpoint is objective response rate as determined by RECIST 1.1 (or MD Anderson criteria for bone-only metastases). Objective response rate will include confirmed complete response (CR) + confirmed partial response (PR) and will be determined as outlined in section 9.

# 12.2.2 Definition of Secondary Endpoints

- Safety of olaparib, defined as rates of Grade 1-5 toxicity according to CTCAE v4.03.
- PFS, which is defined as the time from initiation of treatment to death or progression, depending on which occurs first (as defined by RECIST 1.1).
- Overall survival (OS), which is defined as the time from initiation of treatment to death.

# 12.3 Sample Size and Accrual

Assume the null hypothesis (P0) of 10% as the response rate (the response rate with standard cytotoxic chemotherapy in this setting), a sample size of 27 achieves 81% power to detect a difference (P1-P0) of 18% (that is, P1=28%) using a one-sided exact test with a target significance level of 0.05. The actual significance level achieved by this test is 0.0471. The sample size may be inflated to 30 if replacement of subjects is needed due to early withdrawals or unevaluable subjects.

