#### 4. SUBJECT REGISTRATION

All subjects must be registered through HCRN's electronic data capture (EDC) system. Subjects will be considered registered when an "on study" date is entered into the EDC system.

Subjects must be registered prior to starting protocol therapy and begin study treatment within 7 business days of registration.

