# 12.4 Data Analysis Plans

#### 12.4.1 Analysis Plans for Primary Objective

Any subjects who receive at least one dose of treatment on this protocol will be included in the analysis of the objective response rate. Patients who discontinue treatment prior to the first response assessment will be defined as "non-evaluable" but will be included in the denominator. The objective response rate and its associated 95% confidence interval will be constructed based on the exact binomial test due to the small sample size.

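### The 81% power and 0.0471 level in Section 12.3 hold for 27 analysed subjects only; replacing a dosed subject raises the analysed number to 28-30, where the test needs 7 responders and power is 70.6-77.6% at best

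*Combined protocol and SAP*

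**What the plan says.** Section 12.3 (Sample Size and Accrual) takes a null response rate of 10% and an alternative of 28%. It says that "a sample size of 27 achieves 81% power to detect a difference (P1-P0) of 18" percentage points, "using a one-sided exact test with a target significance level of 0.05", and that "The actual significance level achieved by this test is 0.0471". The same paragraph continues: "The sample size may be inflated to 30 if replacement of subjects is needed due to early withdrawals or unevaluable subjects". The synopsis gives N = 30 without qualification.

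Section 12.4.1 (Analysis Plans for Primary Objective) fixes who is counted: "Any subjects who receive at least one dose of treatment on this protocol will be included in the analysis of the objective response rate". It adds: "Patients who discontinue treatment prior to the first response assessment will be defined as 'non-evaluable' but will be included in the denominator". On the method it says: "The objective response rate and its associated 95% confidence interval will be constructed based on the exact binomial test".

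Section 4 (Subject Registration) separates registration from first dose: "Subjects must be registered prior to starting protocol therapy and begin study treatment within 7 business days of registration". A subject can therefore be registered and leave before dosing.

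The documents state no responder cutoff at any sample size, and no power or level for 28, 29 or 30 subjects.

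**The concern.** The replacement sentence in 12.3 reads as a way to keep 27 usable subjects. That works only if the replaced subject leaves the denominator. Under 12.4.1 a dosed subject never leaves it, so the replacement is added to the count. An unevaluable subject is one of the cases that 12.3 names as a reason for replacement, so this is the ordinary use of the rule.

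Two things are at stake. First, an exact test on so few subjects moves in steps: one more subject can raise the required number of responders and lower the power, so a figure for 27 cannot be carried over to 28. Second, because no cutoff is written down, someone could derive 6 responders from n = 27 and apply it at a larger n, where it exceeds the 0.05 target.

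**Working it through.** **Inputs.** From 12.3: P0 = 0.10, P1 = 0.28, one-sided exact binomial test, target level 0.05, n = 27, ceiling 30. From 12.4.1: all dosed subjects form the denominator.

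**Formulas.** For X ~ Binomial(n, p), the cutoff r is the smallest integer with P(X ≥ r | n, 0.10) ≤ 0.05. The achieved level is P(X ≥ r | n, 0.10) and the power is P(X ≥ r | n, 0.28).

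**Step 1: the plan's own figures.** At n = 27, r = 6. The level is 0.04706, which rounds to the stated 0.0471. The power is 0.8093, which rounds to the stated 81%. Both reproduce.

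**Step 2: the number analysed after replacement.** If k dosed subjects are replaced, n = 27 + k, so k = 1, 2, 3 gives 28, 29, 30. A replaced subject who was never dosed is outside the 12.4.1 set and adds nothing to n.

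**Step 3: the same test at each n**, with a 28% response rate in all dosed subjects.

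| n analysed | Cutoff | Achieved level | Power | Level if 6 were kept |
|---|---|---|---|---|
| 27 | ≥ 6 | 0.0471 | 80.9% | 0.0471 |
| 28 | ≥ 7 | 0.0179 | 70.6% | 0.0550 |
| 29 | ≥ 7 | 0.0216 | 74.3% | 0.0637 |
| 30 | ≥ 7 | 0.0258 | 77.6% | 0.0732 |

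At n = 28 a cutoff of 6 has level 0.0550, above 0.05, so the cutoff must move to 7. Against n = 27, power falls by 80.9 − 70.6 = 10.3 points at 28, by 80.9 − 74.3 = 6.6 points at 29 and by 80.9 − 77.6 = 3.3 points at 30.

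**Step 4: sensitivity.** Step 3 lets the replaced subjects respond at 28%. A subject who stopped before the first assessment is more likely to count as a non-responder. If the 1 to 3 replaced subjects contribute no responses and the other 27 respond at 28%, power is P(X ≥ 7 | 27, 0.28) = 66.5% at each n from 28 to 30. Step 3 is the favourable case.

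**Step 5: the interval.** Section 12.4.1 does not say whether its 95% interval is one- or two-sided.
- If it is two-sided Clopper-Pearson, the lower limit is the 0.025 quantile of Beta(x, n − x + 1): 8.6% for 6/27, 11.1% for 7/27, 10.7% for 7/28, 10.3% for 7/29, 9.93% for 7/30 and 12.3% for 8/30. It excludes 10% from 7 responders at n = 27-29 and from 8 at n = 30.
- If a one-sided 95% lower bound is meant (0.05 quantile), 6/27 gives 10.1% and 7/30 gives 11.5%, in agreement with the test.

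**The case against.** The strongest reply is that nothing in 12.3 is miscalculated. The paragraph ties its power and level to 27 subjects and claims nothing for 28-30. The primary objective is estimation, 12.4.1 reports a rate with an exact interval, and no responder count triggers a decision at any n. On this view the step from 6 to 7 alters no prespecified action, and the loss is only the discreteness of the test: power is back to 80.6% at n = 31. All of this is accurate, and it limits the point. It does not remove it. The plan justifies its size by a test with a stated power and level, and the same paragraph permits sizes at which those figures fail. The recovery at 31 lies one subject above the ceiling.

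It is also fair that replacement is conditional, and that early withdrawal may include subjects who were registered but never dosed. For them the stated figures stand.

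A reader might infer three stronger things that the documents do not support:
- That the 12.3 arithmetic is wrong. It reproduces.
- That the type I error is inflated or the primary interval is invalid. With the cutoff recalculated the test is conservative at 28-30, and the exact interval is valid at any n. The level exceeds 0.05 only if someone carries a cutoff of 6 forward, which the plan does not instruct.
- That the one-sided test and the reported interval contradict each other. That depends on a two-sided interval, which 12.4.1 does not specify, and nothing in the plan promises that the two agree.

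**Conclusion.** The point stands in limited form. The stated power and level, and the cutoff of 6 that they imply, apply to 27 analysed subjects. They do not apply once a dosed subject has been replaced under 12.3. In that case the cutoff is 7. The achieved level is 0.0179 to 0.0258, and power is 70.6% to 77.6% with a 28% response rate in all dosed subjects, or 66.5% if the replaced subjects are non-responders and the other 27 respond at 28%. None of the permitted larger sizes reaches the stated 81%.

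The conclusion assumes that the one-sided exact 0.05 test of 12.3 is applied to the 12.4.1 denominator, and that at least one replaced subject was dosed. It does not affect the validity of the response-rate estimate or its interval. It should be fixed because the remedy is only text, and because a cutoff set after a borderline result would be open to dispute.

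**What to change.** Amend 12.3 to say, in substance:

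> The power and level given above apply to 27 analysed (dosed) subjects. A replaced subject who was dosed stays in the primary denominator (Section 12.4.1), so 28, 29 or 30 subjects may be analysed. With P1 = 28% in all dosed subjects, the cutoff, achieved level and power of the one-sided exact test are: n = 27: ≥ 6, 0.0471, 80.9%; n = 28: ≥ 7, 0.0179, 70.6%; n = 29: ≥ 7, 0.0216, 74.3%; n = 30: ≥ 7, 0.0258, 77.6%. If the 1-3 replaced subjects count as non-responders and the other 27 respond at 28%, power is 66.5% at n = 28-30.

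Align the synopsis N = 30 with this text: 27 planned, up to 30 with replacement.

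A sentence on the interval is optional and must be conditional: if the 12.4.1 interval is two-sided Clopper-Pearson, it excludes 10% from 7 responders at n = 27-29 and from 8 at n = 30.

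The cost is wording in two places. No patients, data or analyses are added, and the replacement and denominator rules stay as they are. The drawback is that the stated power becomes less favourable; the text discloses the loss and does not recover it.
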